4.2 Handling of dropouts or missing data

4.2.1 Strategy for handling missing data for efficacy analyses

Different approaches will be used to handle missing data including how the Intercurrent events will be considered (Section 3.4).

In this section, 3 terms will be defined for binary endpoints:

- Non-composite binary endpoint: Binary endpoints derived based on 1 continuous measurement (eg, PASI90).
- Composite binary endpoint: Binary endpoints derived based on several continuous measurements (eg, ACR50).
- Composite continuous endpoint: Continuous endpoint derived based on several continuous measurements (eg, PASDAS).

The table below summarizes all continuous endpoints (excluding composite continuous endpoints) along with their observed ranges and indicate whether they are represented by an integer value. These endpoints will be analyzed and / or used in the derivation of composite or non-composite endpoints:

Table 7–1: List of non-composite continuous efficacy endpoints

Efficacy endpoint	Minimum	Maximum	Integer Value
BASDAI	0	10	
EQ-5D-3L dimension scores	1	3	Yes
EQ-5D-3L (VAS)	0	100	Yes
FACIT-Fatigue subscale score	0	52	
HAQ-DI	0	3	
hs-CRP	LLOQ/2 where LLOQ=0.10mg/L	No maximum	

Efficacy endpoint	Minimum	Maximum	Integer Value
IGA	0	4	Yes
LDI	0	No maximum	
LEI	0	6	
Tender dactylitis count	0	20	Yes
mNAPSI	0	13	Yes
PASI	0	72	
PGA-Arthritis / PhGA-Arthritis	0	100	Yes
PGA-PsA / PhGA-PsA	0	100	Yes
PsAID-12	0	10	
PsAQoL	0	20	
PtAAP	0	100	Yes
SF-36 ^a			
Physical Functioning (PF)	19.26	57.54	
Role Physical (RP)	21.23	57.16	
Bodily Pain (BP)	21.68	62.00	
General Health (GH)	18.95	66.50	
Vitality (VT)	22.89	70.42	
Social Functioning (SF)	17.23	57.34	
Role Emotional (RE)	14.39	56.17	
Mental Health (MH)	11.63	63.95	
Physical component summary (PCS)	5.02	79.78	
Mental component summary (MCS)	-3.33	80.09	
SPARCC	0	16	
TJC / SJC	0	68/66	
WPAI-SHP	0	100	

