4.2.2.2.1 Non-Composite binary endpoints

For non-composite binary endpoints, the MI method will be applied as follows based on raw values:

- Step 1: Imputation of missing data using MI:

Create datasets, one for each treatment group, of subjects with observed values and missing values (needing estimation by MI). For the imputation step, missing values will be separated into 2 categories: intermittent missing values (ie, missing values for a given subject that has available data before and after the missing timepoint, including missing value at Baseline) and monotone missing values (ie, where all subject data is missing after a given time point). Datasets should be designed in a horizontal structure meaning that each subject should be present in a single observation, with a set of values, one for each scheduled visit where the endpoint is supposed to be collected according to the protocol (this excludes the unscheduled visits).

Datasets should also be sorted by subject number before proceeding with the MI process.

- For the intermittent missing values**, the missing value in each dataset will be filled in using the Markov-Chain Monte Carlo (MCMC) method with multiple chains, monotone missing data imputing pattern, and non-informative priors for all parameters. Unless specified differently, the first 200 iterations will not be used (the ‘burn-in’ option). A total of 100 sets of imputations will be performed. The seed used for these imputations will be 2017 and all other MI procedures described in this SAP will use this same seed as well. The procedure will be performed for each treatment group separately.

The resulting 100 imputed data sets will have a monotone missing pattern and will be imputed using a method for monotone missingness:

- For monotone missing data**, one monotone regression will be used to impute missing data. A separate regression model is estimated for each variable with missing values (ie, measurement at each time point). Based on the resulting model, a new regression model is then drawn and is used to impute the missing values for the variable. Since the data set has a

monotone missing data pattern, the process is repeated sequentially for variables with missing values. The procedure will be based on the 100 imputed datasets generated from the MCMC procedure and will be performed for each treatment group separately by imputation.

The SAS® PROC MI procedure will be used for the imputation.

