In both cases, the imputation model will include the randomization strata as stratification variables (region and prior TNF α inhibitor exposure), the value at Baseline and at each post-Baseline visit (up to the week of interest). The imputation model based on the MCMC method will only allow joint multivariate normal variables. For the MCMC method (when imputing intermittent missing values), randomization strata will be re-coded as indicator variables, and will be always specified in the following order if they are retained in the model:

- North America region (1 for North America, 0 otherwise)
- Western Europe region (1 for Western Europe, 0 otherwise)
- Eastern Europe region (1 for Eastern Europe, 0 otherwise)
- Prior TNF α 1 (1 for inadequate response to 1 prior TNF α inhibitor)
- Prior TNF α 2 (1 for inadequate response to 2 prior or more TNF α inhibitors)

No variable needs to be created for the 3rd category of prior TNF α inhibitors (intolerance to TNF α inhibitors) or the 4th region (Asia) which is covered when all above variables are “0”.

The randomization strata (region and prior TNF α inhibitor exposure) may be dropped from the imputation model to facilitate model convergence if required (this will be the case for all imputation models) as described below:

- If the MI fails to converge when adjusting on the stratification variables specified above, or if the percentage of randomized subjects is less than 10% in either of the Asia or Western Europe regions, then the Western Europe and Asia region will be combined and the binary variables for region that will be left in the MI will then be for North America and Eastern Europe regions.
- If after doing that, the MI still fails to converge then all region factors will be removed from the MI.
- If the MI still does not converge after dropping the regions, the remaining stratification variables (Prior TNF α 2,1) will also be removed.
- If a variable is dropped in order to allow convergence for one model in the study, that variable does not have to be dropped from other models in the study of the model converges without dropping the variable. That is, model convergence should be evaluated for each efficacy table independently. Furthermore, this means that a table based on a single timepoint may have different variables in the imputation model than a separate by-visit table for the same variable.

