The post-Baseline values will need to be specified in chronological order after the Baseline value in the imputation model so that the SAS® PROC MI imputes variables from left to right (ie, the Week 4 value will be first imputed using regression based on Baseline value, and then the Week 8 value will be imputed using regression based on Baseline and Week 4 values, etc.). The

resulting datasets for each treatment arm will be combined into 1 complete dataset containing 100 times the number of subjects analyzed.

Note: When imputing missing hs-CRP values, missing values due to values below LLOQ (0.10 mg/L) will be replaced by the midpoint value between 0 and LLOQ prior to running MI.

- **Step 2:** Standard rounding rules will be applied to the imputed values after each SAS® PROC MI. If an imputed value falls outside of the range for the given variable (as listed in [Table 7-1](#)), the value will be updated to be within the predefined range. For example, the imputed value for PASI will be updated to 0 or 72 in the case of an imputed value less than 0 or greater than 72, respectively. For endpoints that can take only integer values (eg, IGA as listed in [Table 7-1](#)), the imputed values will be rounded to the closest integer after each SAS® PROC MI.

Note: For hs-CRP, the lower limit used the midpoint value between 0 and LLOQ. For some parameters, there is not necessarily an upper limit to the imputed value (ie, LDI)

- **Step 3:** On the dataset obtained from Step 2, the binary responder variable will be derived. In practice, the value at the week of interest (eg, Week 16) in the imputed data sets will be used to categorize the subject as a responder or not. If subjects have an IE, then the endpoint at all subsequent visits will be set to “nonresponse” and the following will be performed:
 - When date of visit is available: by comparing IE date vs. date of visit
 - When the date of visit is missing in case of fully imputed data at a visit: by comparing the next visit number after the visit where the last study medication occurs vs. the visit number where data are imputed
- **Step 4:** At each timepoint the (unadjusted) proportion of responders will be calculated by treatment group from the imputed datasets using SAS® PROC FREQ.

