4.2.2.2.4 Continuous efficacy endpoints

For secondary and other continuous efficacy endpoints, the same methods as the ones described above for the non-composite binary endpoints will apply based on the values at the timepoint(s) of interest, with the following differences:

- Step 1: The same imputation procedure as the described in step 1 for the non-composite binary endpoints will be used.

- Step 2: The same rounding rules described in step 2 above for non-composite binary endpoints will be performed.
- Step 3: On the dataset obtained with the imputation number from 1 to 100; change from Baseline will be derived. Simple means and standard errors will be calculated using Rubin's rules (via SAS® PROC MIANALYZE) for each timepoint(s) of interest. For calculation of other descriptive statistics such as the median, min and max, Rubin's rules do not apply. MI estimates will be computed by simply averaging the estimates from the multiple repetitions of the imputation algorithm. For CRP data (that will be presented using the geometric mean and corresponding 95% CI, arithmetic mean, median, Q1, Q3, minimum and maximum). The change from Baseline will be expressed as the ratio to Baseline (value at the visit divided by value at Baseline) in the by-visit summaries. The following approach will be applied:
 - Following the MI procedure, the ratio to Baseline will be calculated for any of the imputed values
 - The natural logarithm of the absolute values and of the ratios to Baseline will be calculated
 - The logged values will be summarized by treatment, visit and imputation
 - The datasets will be combined using PROC MIANALYZE in order to get the mean from the absolute values and ratios to Baseline across imputations
 - The estimates of the mean will be back transformed to obtain the geometric mean on the original scale
 - For the median, Q1, Q3, minimum and maximum the procedure outlined above for the other endpoints will be followed
- Step 4: (for primary and secondary efficacy variables): For each value of the imputation number from 1 to 100, the change from Baseline will be analyzed using an ANCOVA model with treatment group, region, and prior TNF α inhibitor exposure as fixed effects and the Baseline value as covariate. The results obtained from the 100 ANCOVA analyses (ie, the LSM for the treatment difference and the 95% CI for the contrasts) will be combined using Rubin's rules (via SAS® PROC MIANALYZE).

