Once defined, the same delta adjustment value will be applied on the imputed values for the Week 16 visit only. The selected scenario will assume that subjects randomized to BKZ and who have missing data have a lower probability of response compared to subjects randomized to placebo with missing data.

- For ACR components for which high scores are associated with a less favorable outcome, it will mean that:
 - A positive shift is applied to the imputed value for subjects randomized to BKZ in order to increase the imputed value.
 - A negative shift is applied to the imputed value for subjects randomized to placebo in order to decrease the imputed value.

A set of possible values will be first pre-defined for the delta parameter as follows:

- For all ACR components, the value of the initial delta parameter will be equivalent to a specific percentage of the possible range of each component (ie, 5%). For hs-CRP, the range will be based on the log-transformed values at Week 16. The delta parameters for each endpoint are listed in the [Table 7-3](#) .

Table 7-3: Tipping point analysis: Delta parameter for each ACR component

ACR component ¹	Range	Delta
SJC	0-66	3.3
TJC	0-68	3.4
HAQ-DI	0-3	0.15
PtAAP, PhGA-PsA, PGA-PsA	0-100	5

ACR component ¹	Range	Delta
hs-CRP ²	Observed range of the log _e transformed values for all subjects at Week 16	5% of the observed range

¹The shifted imputed value should not exceed the range for the ACR component.

²The delta adjustment will be applied on the log_e transformed imputed and observed values which will then be exponentiated prior to deriving endpoint.

- **Step 4:** Standard rounding rules will be applied to the imputed values. If the SAS® PROC MI yields a value outside of the range for the given component, the value will be updated after the imputation has been performed to be within the predefined range.
- **Step 5:** Repeat steps 1 to 4 for each ACR component. The composite binary endpoint (ACR50) will then be derived based on the multiple shifted imputed data sets obtained for each component.

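### hs-CRP is imputed on the raw scale, floored at 0.05 mg/L and logged only afterwards, which biases the MI-based geometric means downward (minor; primary analysis and hierarchy unaffected)

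*SAP*

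**What the plan says.** Section 4.2.2.2.1 sets the scale: "For non-composite binary endpoints, the MI method will be applied as follows based on raw values". It also sets the distribution: "The imputation model based on the MCMC method will only allow joint multivariate normal variables". Monotone gaps are then filled by linear regression on earlier visits.

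hs-CRP gets two special instructions there, and neither is a transformation. Before imputation, "missing values due to values below LLOQ (0.10 mg/L) will be replaced by the midpoint value between 0 and LLOQ prior to running MI". After imputation, Step 2 deals with a draw as follows: "If an imputed value falls outside of the range for the given variable", it is moved to the limit. The table of ranges in Section 4.2.1 gives the hs-CRP minimum as "LLOQ/2 where LLOQ=0.10mg/L", that is 0.05 mg/L, with no maximum. Step 2 repeats this: "Note: For hs-CRP, the lower limit used the midpoint value between 0 and LLOQ".

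Section 4.2.2.2.4 reuses the same imputation step for continuous endpoints. Only once imputation is finished does it say: "The natural logarithm of the absolute values and of the ratios to Baseline will be calculated". The means of the logs are then back-transformed to geometric means. Section 4.2.2.2.2 imputes each component of a composite separately by the same method. Reference-based MI (Section 4.2.2.3) also works on raw values, with no exception for CRP.

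**The concern.** CRP is positive and right-skewed. The SAP accepts this by reporting a geometric mean, a geometric CV and a ratio to Baseline (Sections 3.1 and 8.1.1.4). A normal draw with the raw mean and SD of such a variable is often negative. Flooring makes it admissible but puts it at an extreme on the scale on which it is summarised: ln 0.05 = -3.0, against ln 4.5 = +1.5 for a value of 4.5 mg/L. A modest share of floored draws therefore pulls the mean of the logs down.

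In ACR response, a floored draw counts as at least 50% CRP improvement unless Baseline CRP is below 0.10 mg/L. At stake are the MI-based CRP tables and, more weakly, any MI analysis that builds a response or score from imputed CRP.

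**Working it through.** The SAP states no CRP mean, spread or missing rate, so it has no figure of its own to reproduce here. From the document I take the raw-scale normal or linear model, the floor of 0.05 mg/L, the log after MI, and arms of 260 and 130 (Section 2.4). The rest is assumed.

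**Step 1: share of draws below the floor.** For log-normal CRP with median M and SD of ln CRP equal to σ, the raw mean is m = M·exp(σ²/2) and the raw SD is s = m·√(exp(σ²) − 1). A normal draw falls below the floor with probability Φ((0.05 − m)/s). With M = 4.5:

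- σ = 0.6: m = 5.39, s = 3.55, Φ(−1.51) = 7%
- σ = 1.0: m = 7.42, s = 9.73, Φ(−0.76) = 22%
- σ = 1.4: m = 11.99, s = 29.6, Φ(−0.40) = 34%

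Medians from 2 to 6 mg/L give nearly the same shares, because the floor is close to zero.

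**Step 2: simulation with regression on earlier visits.** Assumptions: five visits; log-normal CRP with σ 0.8 to 1.2 and between-visit correlation 0.3 to 0.7; Baseline median 5 mg/L; later medians 2.0 (bimekizumab) and 4.5 (placebo); 5% to 15% of Week 16 values missing at random. Imputation was by arm, by Bayesian linear regression on the raw scale floored at 0.05, and was compared with the simulated truth. Across scenarios 11% to 27% of draws were floored. Results at 10% missing and correlation 0.5:

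| Arm | σ | Floored | Geometric mean of imputed values (truth) | Whole-arm geometric mean (truth) |
|---|---|---|---|---|
| Bimekizumab | 1.0 | 20.9% | 1.41 (1.97) | 1.938 (2.002), 3.2% low |
| Bimekizumab | 1.2 | 26.7% | 1.43 (1.99) | 1.945 (2.011), 3.3% low |
| Placebo | 1.0 | 19.9% | 2.67 (4.34) | 4.261 (4.469), 4.7% low |
| Placebo | 1.2 | 25.2% | 2.71 (4.53) | 4.286 (4.511), 5.0% low |

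Hand check, placebo, σ = 1.0: (2.67/4.34)^0.10 = 0.953, about 4.7% low.

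Over all scenarios, the geometric mean of the imputed values was 23% to 32% too low on bimekizumab and 30% to 44% too low on placebo. The whole-arm figure was about 1.5% to 5% and 2% to 8% too low, respectively.

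**Step 3: between-arm ratio** (σ = 1.0, 10% missing). Truth: 2.002/4.469 = 0.448. Raw-scale MI: 1.938/4.261 = 0.455.

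**Step 4: CRP improvement of at least 50%, same scenario.** Among imputed subjects: placebo 34.3% against 29.2% true, bimekizumab 52.2% against 58.0% true. Multiplied by the 10% missing, that is 0.10 × 5.1 = 0.5 and 0.10 × 5.8 = 0.6 points of each arm. Over all scenarios the shift is about 1 point or less of an arm. This concerns one of five measures, of which three are needed in addition to both joint counts. No effect on ACR50 itself was computed.

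**Step 5: the same model on ln CRP.** Floored draws fall to 0% to 0.2%, and the whole-arm geometric mean is within 0.3% of the truth.

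**Step 6: where imputed CRP goes.**

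- By-visit MI summaries of hs-CRP (Section 8.3.2.2).
- DAPSA, DAS28[CRP] and PASDAS, when built from imputed components. DAS28[CRP] and PASDAS use ln(CRP + 1), so a floored draw enters as ln 1.05 = 0.05, far milder than −3.0. DAPSA adds CRP untransformed. These effects were not quantified.
- Supportive ACR50 analyses: modified composite, treatment policy, and the placebo arm of the delta-adjusted tipping point.

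**The case against.** The strongest case against is about reach. The primary ACR50 analysis is non-responder imputation (Section 8.1.2) and uses no imputed CRP. The other hierarchy endpoints are HAQ-DI, PASI90, SF-36 PCS and MDA (Section 4.5), and none of the seven MDA criteria is CRP. By-visit CRP tables are descriptive, observed-case results stand beside them (Section 8.3.2.2), and hs-CRP is not among the variables given nominal p-values (Section 8.3.2.3). An ACR status that can be derived from observed data is not changed by imputation (Section 8.1.1). All of this stands, and it makes the point minor.

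A reader might infer more, and the document does not support it:

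- That a fixed share of draws, say a fifth to a quarter, will be floored. That needs an SD of ln CRP of about 0.94 to 1.08, which the SAP does not state.
- That both arms of the tipping-point analysis are distorted. Step 6 of Section 4.2.2.4 sets bimekizumab subjects with missing data to non-response after the shift. The delta analysis also runs only if the worst-case analysis loses significance.
- That the SAP contradicts itself because it says "For hs-CRP, the range will be based on the log-transformed values at Week 16". That sentence scales a shift applied after imputation, for a variable with no maximum. It does not conflict with imputing on the raw scale.

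Two technical objections stand in part. The simulated CRP was log-normal, so the success of the log model is partly built in; the direction of the raw-scale bias needs only right skew and the floor. Exponentiated draws have no upper limit, and the SAP also reports arithmetic means and maxima of CRP and describes the component ANCOVA on change from Baseline with no log step (Section 8.1.4.4). That is a real cost of the fix, but a small one.

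**Conclusion.** The point holds as a minor correction. Followed exactly, the plan gives MI-based hs-CRP geometric means that are too low in both arms, by the amounts in Steps 2 and 3 of the working. Those amounts rest on the assumed spread, correlation, medians and missing rate. Reference-based MI shares the raw scale but was not simulated.

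No confirmatory result changes. In the supportive MI analyses of ACR50 the effect should be very small. Where both arms are affected, the CRP component is too favourable on placebo and too unfavourable on bimekizumab, so it leans against the active arm and could not create a supportive result.

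**What to change.** Add to Sections 4.2.2.2.1 and 4.2.2.3 that, for hs-CRP:

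1. values below LLOQ are set to 0.05 mg/L;
2. ln(hs-CRP) is taken at every visit before the MCMC, monotone-regression and reference-based steps;
3. the lower bound is applied as ln 0.05;
4. values are exponentiated before ACR response, DAPSA, DAS28[CRP], PASDAS and change from Baseline are derived.

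The cost is one transformation step and a sentence or two of text. Because back-transformed draws are unbounded above, check the largest imputed values and read MI arithmetic means and maxima of hs-CRP beside the geometric mean.

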4.2.2.2 Composite binary endpoints

For composite binary endpoints, the MI method will be applied as follows:

- **Step 1:** The MCMC/monotone regression approach described above in Step 1 for non-composite binary endpoints will be performed separately for each individual component variable.

- **Step 2:** The same rounding rules described in Step 2 above for non-composite binary endpoints will be performed for each component.
- **Step 3:** Based on the multiple imputed data sets obtained for each component, the binary response will be derived as follows:
 - The dataset obtained for each component will be merged by imputation number and subject number
 - On the dataset obtained, the binary endpoint will be derived for each subject/visit based on the component values.
 - If subjects have an IE, then the endpoint at all subsequent visits (from the day after the intercurrent event date, whether the data were observed or not) will be set to “non-response”.
- **Steps 4 and 5:** Same as Steps 4 and 5 above for non-composite binary endpoints ([Section 4.2.2.2.1](#)).

For the primary endpoint, the ‘burn-in’ option in SAS® PROC MI may be set higher than the default value. The goodness-of-fit tests to assess convergence of the MCMC will be provided in a SAS® output.

4.2.2.2.3 Calculation of adjusted responder rates, odds ratio and CIs for binary endpoints.

Estimates of the adjusted responder rates for each treatment group and the associated standard errors are obtained from the logistic regression in Step 5 on the logit scale and as such are assumed to follow a normal distribution. These estimates will be combined using Rubin’s rules and the combined estimates and associated SEs will be used to construct 95% CIs on the logit scale. The combined estimates and 95% CIs on the logit scale will be back transformed using the inverse logit link function to obtain the adjusted responder rates (%) and associated 95% CIs.

Some key points to consider relative to the calculation of the odds ratios and corresponding confidence intervals. As the estimates of the odds ratios from the logistic regression model in step 5 follow a lognormal distribution, a log transformation is needed to normalize these 100 odd-ratio estimates since the procedures for combining results from multiple imputed datasets are based on the assumption that the statistics estimated from each imputed dataset are normally distributed. Therefore, the log of the odds ratio estimates from the logistic regression model are used when combining into a single inference (step 3). Additionally, the standard errors (SE) for the odds ratios are transformed as follows:

$$SE = \frac{\log(UCL) - \log(LCL)}{2Z_{\alpha/2}}$$

where UCL and LCL are the upper and lower confidence limit, respectively, for the CI of the odds ratio from the logistic regression model, and $Z_{\alpha/2}$ is the relevant critical value from the standard normal distribution (1.96 for a 95% CI). The estimates of the log odds ratio for BKZ relative to placebo and the corresponding upper and lower confidence limits will be provided. The odds ratio will be then estimated by exponentiating the estimate of the log odds ratio. The odds ratio and the confidence limits of the odds ratio will be estimated as follows:

$$OR = \exp(\text{Log odds ratio estimate})$$

$$LCL = OR * \exp(-SE * Z_{\alpha/2})$$

$$UCL = OR * \exp(SE * Z_{\alpha/2})$$

where OR is the back-transformed estimate of the odds ratio just described, SE is the standard error of the log odds ratio and $Z_{\alpha/2}$ is the relevant critical value from the standard normal distribution (1.96 for a 95% CI). These calculations will be done such that odds ratios and corresponding CIs are calculated for the odds ratio of BKZ versus placebo.

In addition to calculating the odds ratio, associated CIs, and p-values for the comparisons of BKZ vs. placebo, the estimated proportion of responders (ie, estimated responder rate) and the difference in the proportion of responders between BKZ and placebo will be estimated, along with 2-sided 95% CIs. The creation of the estimates of this difference will be completed using the process detailed below:

1. Use the logistic regression model to calculate:

Least squares mean (LSM) estimates of the log odds of BKZ (G_B) and placebo (G_P), as well as their corresponding standard errors (S_B and S_P , respectively).

Standard error of the LSM estimate of the log odds ratio (S_R)

2. Compute estimates for predicted proportions using the following transformations:

$$P_B = \exp(G_B)/(1 + \exp(G_B))$$

$$P_P = \exp(G_P)/(1 + \exp(G_P))$$

The difference in proportions is then given by:

$$D = P_B - P_P$$

3. Estimate the standard error of D by:

$$SD = \text{sqrt}[P_B^2(1-P_B)^2S_B^2 + P_P^2(1-P_P)^2S_P^2 + P_B(1-P_B)P_P(1-P_P)S_R^2 - P_B(1-P_B)P_P(1-P_P)(S_B^2 + S_P^2)]$$

The MI/MCMC monotone regression method, as previously outlined, will be used to account for missing values. The calculation steps described above will be based on the results provided from the logistic regression model of the multiple imputed datasets. An estimate for the difference in proportions, D, and corresponding standard error, SD, will be computed for each of these datasets. The results from these analyses will be combined into a single estimate of the difference in predicted proportion of response and a 2-sided 95% CI interval using SAS PROC MIANALYZE.

